TEAE:	treatment-emergent adverse event
TEWL:	transepidermal water loss
V:	visit
W:	week
WHO-DD:	world health organisation drug dictionary

1 OVERVIEW AND STUDY PLAN

This statistical analysis plan (SAP) provides a comprehensive and detailed description of strategy and statistical technique to be used to realize the analysis of data for study LPS16764 (short title: Dupilumab-pediatric skin barrier function and lipidomics study in patients with atopic dermatitis – PELISTAD). It is applicable for the analysis for the treatment phase and the analysis for the follow-up period.

The analyses described are based upon the final clinical study protocol V1.0 dated 13 July 2020 and will be prepared in accordance with the international conference on harmonization (ICH) E9 Step 4 version dated 05 February 1998 ([1](#)).

Objectives, endpoints and statistical analyses related to biomarkers (ie, lipidomics, Filaggrin (FLG) genotyping, proteomics, and transcriptomics) will be detailed in a specific dedicated SAP.

The statistical analyses (except biomarkers analyses) will be performed by the Biostatistics department of BIOTRIAL BIOMETRICS in agreement with the Sponsor.

The clinical SAP will be validated and signed before the study database for the treatment phase analysis is locked.

1.1 STUDY DESIGN

Study design

This is a Phase 4 open-label, exploratory study in three sites evaluating the effect of dupilumab on skin barrier function (as measured by transepidermal water loss (TEWL) before and after skin tape stripping [STS]) in pediatric patients aged between ≥ 6 and <12 years old with moderate-to-severe atopic dermatitis (AD) with a healthy volunteer cohort as a reference comparator. Patients with moderate-to-severe AD will be included in the US site and patients with severe AD will be included in the EU site (UK). One more US site was initiated because the recruitment at the first US site was insufficient.

Sample size

Approximately 24 pediatric patients with moderate-to-severe AD will be enrolled. An approximately equal number of age, gender, location of targeted lesion area and site matched healthy volunteers serving as a reference comparator cohort will also be enrolled.

Randomization

Not applicable.

Treatment received

Study participants will be assigned to study intervention as described below:

- Up to 24 pediatric patients with moderate-to-severe AD will receive dupilumab.
- Dose regimen 1: children with baseline $15 \text{ kg} \leq \text{body weight} < 30 \text{ kg}$ will receive a subcutaneous (SC) loading dose of dupilumab 600 mg (2 injections of dupilumab 300 mg) on Day 1 (Week 0), followed by every 4-week SC dosing of dupilumab 300 mg from Week 4 to Week 12.
- Dose regimen 2: children with baseline $30 \text{ kg} \leq \text{body weight} < 60 \text{ kg}$ will receive a SC loading dose of dupilumab 400 mg (2 injections of dupilumab 200 mg) on Day 1 (Week 0), followed by bi-weekly SC dosing of dupilumab 200 mg from Week 2 to Week 14.

The treatment will be given to the pediatric patient (≥ 6 and < 12 years of age) depending on its body weight.

Duration of study period

This is a 32-week study with a 4-week screening period, 16-week treatment phase designed to investigate dupilumab's effect on skin barrier function in approximately 20 pediatric patients with moderate-to-severe AD, and a 12-week follow-up period.

The graphical study design is detailed in [Section 8 \(Appendix A\)](#).

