- Change (percent and absolute) from baseline in POEM (total score) over time.
- Change (percent and absolute) from baseline in CDLQI (total score) over time.
- Change (percent and absolute) from baseline in assessment of worst itch NRS (scale) over time.
- Change (percent and absolute) from baseline in sleep disturbance NRS (scale) over time.
- Change (percent and absolute) from baseline in skin pain NRS (scale) over time.
- Change (percent and absolute) from baseline in photograph outputs (TiVi and skin roughness indexes) obtained from skin imaging over time.
- Correlation between baseline values of TEWL before and after STS, and TEWL AUC in lesional and non-lesional skin of AD patients with the following baseline measures:
 - EASI.
 - Targeted lesion ISS.
 - Image-derived severity score in targeted lesional skin.
 - Quantified epidermal hypertrophy and structure changes in OCT and FTIR.
- Correlation between percent change from baseline in TEWL before and after STS, and TEWL AUC in lesional and non-lesional skin of AD patients at Week 8, Week 16 and Week 28 with corresponding change from baseline in the following measures:
 - EASI.
 - Targeted lesion ISS.
 - Image-derived severity score in targeted lesional skin.
 - Quantified epidermal hypertrophy and structure changes in OCT and FTIR.

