- As an exploratory analysis, the time to improvement of skin barrier function for lesional and non-lesional skin area measured by TEWL will be summarized for the treatment phase. Improvement is defined as time to the first post-baseline day for which at least 1 TEWL measure of a patient is equal or lower than the TEWL median in the matched healthy volunteers over time. Results might be reported through Kaplan-Meier plot in case of high number of events. Time to improvement of skin barrier function for lesional and non-lesional skin area will also be listed.

For the analyses of change (percent and absolute) from baseline in TEWL AUC (a composite measure before and after 5, 10, 15, and 20 STS) for skin barrier function in each skin group over time:

- As all TEWL values are expected to be positive, area under the TEWL curve will be calculated using the trapezoidal method over the 20 STS (measurement at every 5 STS and all other unplanned number of STS) at each visit. For AUC derivation only, TEWL data performed at unplanned number of STS will be used.
- Raw data and change (absolute and percent) from baseline will be summarized with descriptive statistics by skin group and timepoints. For follow-up period data, change from Week 16 (or last visit prior to use of rescue treatment) will also be reported.
- Box plots over time will be generated for absolute change from baseline/Week 16.
- As exploratory analysis, time to improvement of skin barrier function for lesional and non-lesional skin area measured by TEWL AUC will be summarized for the treatment phase. Improvement is defined as time to the first post-baseline day for which TEWL AUC of a patient is equal or lower than the median, of the corresponding TEWL AUC computed in his/her matched healthy volunteer over time. Results might be reported through Kaplan-Meier plot in case of high number of events.

TEWL conditions (ie, room temperature and humidity, etc.) will be summarized with descriptive statistics by timepoint.

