A correlation analysis will also be investigated between baseline values of TEWL (before and after each number of STS), and TEWL AUC in lesional and non-lesional skin of AD patients with the following baseline measures: EASI, targeted lesion ISS, image-derived severity score in targeted lesional skin, and quantified epidermal hypertrophy and structure changes in OCT and FTIR measures. For this analysis, scatterplot to visualize the form of the relationship between variables will be produced for patients' cohort at specific time points: baseline, Week 8, Week 16 and Week 28. Pearson correlation will be assessed at each defined time point for EASI, ISS, photograph outputs, OCT outputs: epidermal thickness, supervidial plexus depth, blood vessel diameter and density, and FTIR measures. Pearson correlation coefficient and p-value will be reported. Spearman's rank correlation will be assessed at each defined timepoint for ISS. Spearman correlation coefficient and p-value will be reported. As an exploratory analysis repeated measures correlation method might be used to assess the overall correlation pooling data from baseline, Week 8, Week 16 and Week 28 (3).

The same approach will be used to investigate the correlation between percent change from baseline in TEWL (before and after each number of STS), and TEWL AUC in lesional and non-lesional skin of AD patients at Week 8, Week 16 and Week 28 with corresponding change from baseline of the aforementioned measures (ie, EASI, targeted lesion ISS ...).

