4.3.4 Additional exploratory analyses

In a similar study conducted by the Sponsor, differences in clinical conditions were also identified between centres (ie, room temperature in a specific centre higher than required by the study protocol). Consequently, the centre effect will be investigated and some covariates (ie, room temperature ...) could be included in the statistical models.

Additionally, the following comparisons will be investigated on ITT population only:

- The comparison in TEWL between Day 1 and Week 16 will be performed by skin group (lesional and non-lesional skin area only), STS and spot using a non-parametric Wilcoxon signed-rank test.
- The comparison in TEWL AUC between Day 1 and Week 16 will be performed by skin group (lesional and non-lesional skin area only) and spot using a non-parametric Wilcoxon signed-rank test.
- The comparison between AD participants (lesional skin area/non-lesional skin area) and Healthy participants will be performed on TEWL data at Week 16 using a non-parametric Wilcoxon signed-rank test.
- The comparison AD participants (lesional skin area/non-lesional skin area) versus Healthy participants will be performed on TEWL AUC data at Week 16 using a non-parametric Wilcoxon signed-rank test.

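### Eligible AD severity differs by site, so the pooled single-visit TEWL-severity correlations can partly reflect centre, and a centre effect examined in AD patients can partly reflect severity

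*SAP*

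**What the plan says.** Section 1.1 describes the design: "This is a Phase 4 open-label, exploratory study in three sites". The severity admitted depends on the site: "Patients with moderate-to-severe AD will be included in the US site", while "patients with severe AD will be included in the EU site (UK". The third site is also in the US: "One more US site was initiated because the recruitment at the first US site was insufficient". Its severity criterion is not given separately; I take it to be that of the first US site.

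Section 4.1.4 lists as an endpoint the "Correlation between baseline values of TEWL before and after STS, and TEWL AUC in lesional and non-lesional skin of AD patients" with EASI, target-lesion ISS, imaging, OCT and FTIR measures. Section 4.3.3.3 gives the method: "Pearson correlation will be assessed at each defined time point for EASI, ISS, photograph outputs" and the OCT and FTIR measures, with Spearman also for ISS. Coefficients and p-values are reported at baseline and Weeks 8, 16 and 28. No centre term, stratum or partial correlation is mentioned.

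Section 4.3.4 recalls a similar sponsor study in which one centre's room was warmer than its protocol required, and concludes that "the centre effect will be investigated and some covariates", with room temperature as the example, could enter the models. It names neither the model nor the cohort for this check, and does not mention severity. Section 4.3.3.2 says that TEWL conditions such as room temperature and humidity "will be summarized with descriptive statistics by timepoint", with no split by centre.

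**The concern.** Two things may differ between the UK and US patients: how severe the disease is, by eligibility, and how TEWL reads, through room conditions. If both do, pooling the centres turns them into a TEWL-severity correlation even when there is none within any centre. If the UK site happens to read low, pooling instead hides a real one.

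The converse holds for the centre check. Suppose TEWL rises with severity. A UK-US difference among AD patients then appears even in identical rooms, and it could be taken for a room effect and adjusted away.

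What is at stake is the reading of the second tertiary objective in section 1.2.3, the association of TEWL with disease severity, where it rests on values at one visit.

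**Working it through.** **The plan's own figure.** The only stated number is the enrolment target in section 1.3: 20 / (1 − 0.15) = 23.5, rounded up to 24. It reproduces, and the point does not turn on it.

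**What the SAP does not give.** Patients per site, the severity mix at the US sites, and any centre shift in TEWL in this trial. All three are assumed below.

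**Induced correlation.** Let p be the UK share of AD patients, and a and b the UK-US shifts in severity and TEWL, in within-centre SD. With no within-centre association,

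r = p(1−p)ab / √[(1 + p(1−p)a²)(1 + p(1−p)b²)].

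For a = b this is p(1−p)a² / (1 + p(1−p)a²). Rejection rates are from 40,000 simulated trials per row, with 24 patients and normal data:

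| UK share | Shift in both (SD) | Pooled r | Pooled test, p < 0.05 |
|---|---|---|---|
| 1/3 | 0.5 | 0.0556 / 1.0556 = 0.05 | 5.7% |
| 1/3 | 1 | 0.2222 / 1.2222 = 0.18 | 13.8% |
| 1/3 | 1.5 | 0.5 / 1.5 = 0.33 | 38.8% |
| 1/2 | 0.5 | 0.0625 / 1.0625 = 0.06 | 5.9% |
| 1/2 | 1 | 0.25 / 1.25 = 0.20 | 15.9% |
| 1/2 | 1.5 | 0.5625 / 1.5625 = 0.36 | 44.5% |

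The centre-adjusted test rejects in 4.8% to 5.2% throughout.

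**Masking.** With a true within-centre r of 0.5 and opposing shifts of 1 SD, pooled r is (0.5 − 0.2222) / 1.2222 = 0.23 at a UK share of 1/3, and (0.5 − 0.25) / 1.25 = 0.20 at 1/2.

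**Dependence on the US severity mix.** A second model takes 20 evaluable patients, severe and moderate disease 2 SD apart on the severity score, a TEWL centre shift of 1 SD and no true link (4,000 simulated trials per cell):

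| US patients severe | 10 of 20 in the UK: mean r, p < 0.05 | 6 of 20 in the UK: mean r, p < 0.05 |
|---|---|---|
| 0% | 0.33, 29% | 0.29, 24% |
| 30% | 0.23, 16% | 0.20, 13% |
| 60% | 0.14, 9% | 0.12, 7% |
| 100% | 0.00, 5% | 0.00, 5% |

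With no centre shift (30% severe, 10 of 20 in the UK), rejection is also 5%.

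**Centre check in AD patients.** Take identical rooms, a TEWL slope on severity of 0.5 per SD, the same 2 SD gap and 10 of 20 patients in the UK. The expected spurious UK-US difference is 0.5 × 2 × (1 − share of US patients severe) = 1.0, 0.7, 0.4 and 0 residual SD at 0%, 30%, 60% and 100% severe. Simulation gives 1.01, 0.70, 0.40 and 0.01, with p < 0.05 in 49%, 25%, 12% and 5%. With the severity score in the model the difference is about 0.

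**What the healthy volunteers can show.** With about 24 volunteers split 8/16, the standard error of a UK-US difference is √(1/8 + 1/16) = 0.43 SD; split 12/12 it is √(1/12 + 1/12) = 0.41 SD. The 95% interval is about ±0.8 to 0.9 SD.

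**The case against.** The strongest reply is that every size above is assumed. The room-temperature problem occurred in a different study. The US sites may enrol mostly severe patients, and shifts of 0.5 SD do almost no harm. That stands: the SAP shows a route to bias, not its amount.

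A reader might infer that the whole tertiary objective on TEWL and severity is unreliable, or that the primary result is confounded. The SAP does not support this. The primary endpoint is a within-patient percent change. A stable additive centre offset cancels in absolute change and a stable multiplicative one in percent change, so the change-from-baseline correlations are much less exposed. The optional repeated-measures correlation works within patients.

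A reader might also infer that the SAP ignores centre or leaves the volunteers unused. That goes too far. Section 4.3.4 commits to investigating the centre effect. Section 4.3.3.1 lets site enter the repeated-measures model if baseline is heterogeneous. That model has type of skin as a factor, and section 3 counts healthy skin among the three groups, so volunteers could inform a site term. But the option concerns percent change from baseline and does not reach the correlations in section 4.3.3.3. Baseline TEWL in that model is no clean stand-in for severity either, because room conditions move it too.

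Finally, adjusting for centre removes genuine between-centre severity signal and narrows the severity range within the UK site. If rooms are comparable, the pooled value is the more informative. This argues against making the adjusted value decisive, but not against showing it. Nor do the volunteers settle the centre effect: their interval is too wide to resolve 0.5 SD, and a room effect on normal skin need not equal that on lesional skin.

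**Conclusion.** The point holds for correlations of values at baseline or a single visit, and for a centre effect examined in AD patients without a severity term. It rests on three statements in the SAP: severity eligibility tied to site, an expectation that centres differ in measuring conditions, and pooled correlations with p-values and no centre term. The summary of room conditions by timepoint alone would not reveal the difference.

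The size is conditional. It is negligible at shifts of 0.5 SD in both variables, moderate at 1 SD (r about 0.2, rejection about 15%) and substantial at 1.5 SD (r about 0.35, rejection about 40%). It is nil if centres measure alike or the US patients are nearly all severe. The analyses are exploratory and unpowered, so this affects interpretation and no confirmatory conclusion. It is an inexpensive improvement worth making before database lock, when the choice to adjust cannot yet depend on the results.

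**What to change.** - **Section 4.3.3.3:** beside each pooled TEWL-severity correlation, report the partial correlation with centre as a factor. State that the pooled value is interpreted with caution where the two diverge materially. Do not make the adjusted value automatically decisive.
- **Section 4.3.4:** when the centre effect is examined in AD patients, include baseline EASI, which is already collected. Show the centre difference in the site-matched healthy volunteers with its confidence interval, labelled as supportive and imprecise.
- **Section 4.3.3.2:** summarise TEWL room conditions by centre and timepoint.

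**Cost:** SAP wording, a few more table columns, and one or two degrees of freedom. The adjusted correlations are somewhat less precise and lose some genuine between-centre severity signal, which is why both values should be shown. No new data are needed.

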1.2 OBJECTIVES

1.2.1 Primary objective

The primary objective of this study is to evaluate changes in skin barrier function with TEWL assessed after STS in predefined lesional skin in pediatric patients with moderate-to-severe AD treated with dupilumab.

1.2.2 Secondary objectives

The secondary objectives are:

1. To evaluate changes in skin barrier function with TEWL assessed after STS in predefined lesional and non-lesional skin in pediatric patients with moderate-to-severe AD treated with dupilumab in reference to normal skin of healthy volunteers.
2. To evaluate time course of change in skin barrier function with TEWL assessed before and after STS in predefined lesional and non-lesional skin in pediatric patients with moderate-to-severe AD during dupilumab treatment phase and follow-up period in reference to normal skin of healthy volunteers.

1.2.3 Tertiary/exploratory objectives

The clinical tertiary/exploratory objectives are:

1. To evaluate dupilumab treatment effect on epidermal hypertrophy and structure of skin barrier changes measured by optical coherence tomography (OCT) and fourier-transform infrared (FTIR) spectroscopy in both predefined lesional and non-lesional skin in pediatric patients with moderate-to-severe AD during dupilumab treatment phase and follow-up period in reference to normal skin of healthy volunteers.
2. To explore the association of skin barrier function measured by TEWL with disease impact assessed by standard AD severity assessments (Eczema area and severity index [EASI], and individual signs score [ISS]), patient reported outcomes (PRO) (patient oriented eczema measure [POEM], children dermatology life questionnaire index [CDLQI], worst itch numerical rating scale [NRS], sleep disturbance NRS, skin pain NRS), standardized photos, and the skin barrier hypertrophy and structure profiles assessed by OCT and FTIR.

1.3 DETERMINATION OF SAMPLE SIZE

No formal sample size calculation was performed for this exploratory study. It was based on medical/clinical judgment and is consistent with the sample size from similar studies in the literature (2).

Allowing for drop-out rate of 15%, a total of approximately 24 pediatric patients with moderate-to-severe AD will be enrolled to achieve 20 evaluable patients. An approximately equal number of age, gender, location of targeted lesion area and site matched healthy volunteers serving as a reference comparator cohort will be enrolled. Any drop-out healthy volunteer for whom the matched patient is considered as evaluable will not be replaced.

1.4 STUDY PLAN

The study will comprise of:

- Screening period: Up to 4 weeks (Day -28 to Day -1) from signing the informed consent.
- Baseline visit (Week 0, Day 1): Participants who remain eligible will be enrolled.
- A 16-week open-label treatment phase for AD patients and a 16-week observation period for healthy volunteers.
- Follow-up period for 12 weeks after the end of treatment (EoT) visit (Week 16). Dupilumab may be used as a rescue therapy for AD patients, if needed during follow-up period.

Schedule of activities in pediatric patients and healthy volunteers are detailed in [Section 8](#) ([Appendix B](#) and [Appendix C](#)).

1.5 MODIFICATIONS FROM THE PROTOCOL

The following changes are added compared to the planned analysis detailed in the study protocol:

- Overall addition: additional information to display on standard TFLs due to COVID19 flags.
- Addition of listing of participants and visits with reasons of exclusion for mITT population (see [Section 4.3.1.3](#)).
- Removing of the listing of other baseline characteristics (see [Section 4.3.2.1](#)).
- Due to strong variability between the 3 adjacent spots in a similar study conducted by the Sponsor, the mean of the 3 adjacent spots will not be appropriated. The analysis will be performed for each spot separately at a visit before/without STS measurement (see [Section 4.3.2.2](#) and [Section 4.3.3.2](#)).
- Update in the Baseline definition for efficacy: the value at Day 1 will be considered as baseline value (or value at Screening if the one at Day 1 is not available). For participants with a value at Day 1 collected after and close to the investigational medicinal product (IMP), the value at this visit could be considered as baseline (judged by clinicians without impact on statistical analysis) (see [Section 4.3.2.2](#)).
- If a change in spot anatomical location changed versus Day 1 is identified and assessed by the study team as having a significant impact on skin barrier, only visits prior to the location change will be considered in the statistical analysis of TEWL data (see [Section 4.3.3.1](#) and [Section 4.3.3.2](#)).
- Use of a repeated measures mixed model to analyze primary and main secondary endpoints (see [Section 4.3.3.1](#)).
- Addition of descriptive statistics on TEWL conditions (see [Section 4.3.3.2](#)).
- Except for AUC derivation, TEWL data performed at unplanned number of STS will not be used (see [Section 4.3.3.2](#)).
- Tertiary/exploratory endpoints will be analyzed also on the ITT population (see [Section 4.3.3.2](#)).
- The following analyses will be added on ITT population only (see [Section 4.3.4](#)):
 - The comparison in TEWL between Day 1 and Week 16 will be performed by skin group (lesional and non-lesional skin area only), STS and spot using a non-parametric Wilcoxon signed-rank test.
 - The comparison in TEWL AUC between Day 1 and Week 16 will be performed by skin group (lesional and non-lesional skin area only) and spot using a non-parametric Wilcoxon signed-rank test.
 - The comparison AD participants (lesional skin area/non-lesional skin area) versus Healthy participants will be performed on TEWL data at Week 16 using a non-parametric Wilcoxon signed-rank test.

- The comparison AD participants (lesional skin area/non-lesional skin area) versus Healthy participants will be performed on TEWL AUC data at Week 16 using a non-parametric Wilcoxon signed-rank test.
- Additional statistical analyses could be envisaged as the correlation analysis between the primary endpoint and quantitative global scores of standard AD severity assessments and PRO and the investigation of centre effect due to differences in clinical conditions observed in the similar study conducted by the Sponsor (see [Section 4.3.4](#)).

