4.3.3 Analyses of evaluation variables

4.3.3.1 *Analysis of main evaluation variable(s)*

The primary endpoint will be analyzed on the mITT population. As a sensitivity analysis, it will also be analyzed based on the ITT population.

The calculation of changes (absolute and percent) from baseline will be based on the same number of STS (ie, for absolute change from baseline after 5 STS at W16: Change TEWL at W16 after 5 STS = TEWL value at W16 after 5 STS – TEWL value at baseline after 5 STS).

If a change in spot anatomical location changed versus Day 1 is identified and assessed by the study team as having a significant impact on skin barrier, only visits prior to the location change will be considered in the statistical analysis of TEWL data. Raw data and change (absolute and percent) from baseline will be summarized with descriptive statistics by timepoint.

Profiles over time (from baseline to Week 16) will be generated for individual values (spaghetti plot).

For information purpose as study is not powered (no multiplicity correction will be applied):

- For each number of STS, the evolution of the percent change from baseline over time will be analyzed using a repeated measures analysis of variance with visit, type of skin, interaction between visit and type of skin, age, and baseline value as fixed effects and subject identifier as random effect, at a Type 1 error level of alpha=0.05. In case of heterogeneity at baseline, additional covariates (ie, site, race ...) could be added in this statistical model.
- The following covariance structures will be tested in the REPEATED statement of the PROC MIXED: un, vc and cs at least. The structure with the smallest Bayesian information criteria will be selected for the final model.
- Point estimate and two-sided 95% confidence interval and corresponding two-sided p-value will be reported for each effect. No comparison will be performed.
- If assumption of normal distribution is strongly violated, transformation method could be used: eg, log transformation; normality assumption will be assessed through quantile-quantile plot and Shapiro-Wilk test at 5% Type I error.

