- a For the purpose of this study, any female who has had her first menstrual period (menarche) and is sexually active will be considered to be of childbearing potential. Female patients who are not of childbearing potential at the start of the study but have the onset of menarche during the course of the study and are sexually active will also have to follow adequate birth control methods to continue participation in the study. These females must have a negative urine β -HCG pregnancy test at screening and at each visit. Pregnancy will lead to definitive treatment discontinuation in all cases.
- b Emollients should NOT be applied from Day -7 to the EoS (Week 28) to the targeted, predefined skin areas that will be used for TEWL assessment. Participants should not take showers or soak in a bathtub within 6 hours before TEWL assessment. Emollients for use during the study will be provided by the study site to study participants. Use of emollients should be documented in a diary provided by the study site.
- c TEWL will be measured at each of the 3 closely adjacent spots within the predefined skin areas at all visits without STS and before STS at visits with STS.
- d TEWL will be conducted before STS and then after 5, 10, 15, and 20 STS for skin barrier function assessment in normal skin and at the same location as for the lesional skin in the matching AD patient. All skin tape strips will be collected and stored.
- e At Weeks 0, 8, 16, and 28, STS will be conducted on the first spot within the predefined skin area. At Week 2 STS will be conducted on the second spot within the predefined skin area. At Weeks 4, 12, and 22 STS will be conducted on the third spot within the predefined skin area. TEWL will be assessed in NORMAL skin before STS and 5, 10, 15, and 20 STS. All skin tape strips should be collected and stored.
- f In case STS assessment is to be conducted at an unscheduled visit or at a premature end of treatment visit the assessment should be conducted at that spot of the skin area, for which the period passed since the last STS assessment is the longest.
- g OCT will be done before STS/TWL, and FTIR will be done before and during STS.
- h Vital signs, including heart rate, systolic and diastolic blood pressure (mmHg), pulse rate (beats per minute), body temperature ($^{\circ}$ C), and respiratory rate will be measured.
- i Limited to skin-related physical examination at baseline, EoT visit (Week 16), and EoS (Week28).

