1.2 STUDY DESIGN

[figure not shown]
LPS16764 is a Phase 4 open-label, exploratory study in two sites evaluating the effect of dupilumab on skin barrier function in pediatric patients aged between ≥ 6 and < 12 years old with moderate-to-severe AD. A healthy volunteer cohort will be enrolled as a reference comparator matched to AD for age-, gender-, study-site and sampling will be matched on targeted lesion area. Approximately 24 pediatric patients with moderate-to-severe AD will be enrolled to achieve 20 evaluable patients. These enrolled AD patients will receive Investigational medicinal product (IMP) dupilumab treatment during the study. Approximately 24 healthy volunteers will be enrolled to achieve 20 evaluable subjects. These enrolled healthy volunteers will not receive any IMP treatment during the study.

The maximum study duration per participant will be 32 weeks. The study will comprise of:

- Screening period 1 (Day -28 to Day -1): Participants will be evaluated according to
- Inclusion and exclusion criteria.
- Baseline visit (Week 0, Day 1): Participants who remain eligible will be enrolled.
- A 16-week treatment phase for AD patients and a 16-week observation period for healthy volunteers.
- A 12-week follow-up period.

Biomarker assessment based on lipidomics, proteomics, and transcriptomics in STS samples will be conducted at baseline (Week 0, Day 1), Week 2, Week 4, Week 8, Week 12, EoT at Week 16, and Follow-ups at Week 22 and Week 28.

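### Healthy skin is location-matched only to the patient's lesional area, yet it is also the unadjusted Week 16 and time-to-improvement reference for non-lesional skin, so those exploratory contrasts can mix body site with disease

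*SAP*

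**What the plan says.** **Where healthy skin is measured.** Section 1.3 of the clinical SAP plans for "age, gender, location of targeted lesion area and site matched healthy volunteers serving as a reference comparator cohort". Appendix C, footnote d, places the healthy TEWL and tape-stripping measurement "in normal skin and at the same location as for the lesional skin in the matching AD patient". The biomarker SAP, section 1.2, agrees: "study-site and sampling will be matched on targeted lesion area". Section 3 of the clinical SAP defines three skin groups, only one of them healthy. No second healthy area is matched to the patient's non-lesional area.

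**What that area is used for.** Secondary objective 1 (section 1.2.2) concerns both lesional and non-lesional skin in patients "treated with dupilumab in reference to normal skin of healthy volunteers". Section 1.5 announces the test: "The comparison AD participants (lesional skin area/non-lesional skin area) versus Healthy participants will be performed on TEWL data at Week 16". Section 4.3.4 is the operative text. It prescribes a Wilcoxon signed-rank test on the ITT population, for TEWL and for TEWL AUC. Section 4.3.3.2 defines improvement of both lesional and non-lesional skin as reaching the median TEWL, or TEWL AUC, of the matched healthy skin.

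**How location is treated elsewhere.** Sections 4.3.3.1 and 4.3.3.2 discard visits after a spot has moved from its Day 1 location if the move is "assessed by the study team as having a significant impact on skin barrier".

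**The concern.** The SAP controls location in two places: between lesional and healthy skin, by matching, and within a participant over time, by the location-change rule. It does not control location between non-lesional and healthy skin, although it prescribes that comparison.

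The exposed analyses use raw levels. A signed-rank test on Week 16 TEWL carries any body-site difference in full and takes no covariate. A healthy threshold taken from another region makes improvement of non-lesional skin come too early or too late.

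At stake is how non-lesional skin is read against normal skin under secondary objective 1. An apparent residual barrier defect, or an apparent normalisation at Week 16, might be a property of the body site. The error can go either way.

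**Working it through.** **1. The SAP's own figure.** The only related number is the enrolment target in section 1.3: 20 / (1 − 0.15) = 23.5, rounded up to 24. It reproduces, but the point does not depend on it. The SAP gives no SD, effect size or body-site difference.

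**2. Comparisons set side by side.**

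| Comparison | Scale | Is location controlled? |
|---|---|---|
| Lesional, baseline to Week 16 (primary) | Percent change within patient | Yes, same area; visits after an impactful move are dropped |
| Lesional vs healthy, Week 16 | Raw TEWL, AUC | Yes, by matching |
| Non-lesional vs healthy, Week 16 | Raw TEWL, AUC | Not in the SAP |
| Non-lesional time to improvement | Raw level against healthy median | Not in the SAP |
| 4.3.3.1 model | Percent change from own baseline | Each area is compared with itself |

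**3. Why raw levels are exposed and percent change largely is not.** Let a body region multiply TEWL by a stable factor r, and let a and b be the Week 16 and baseline values without it. The raw Week 16 value becomes r·a, so r enters the contrast with healthy skin. The percent change is (r·a)/(r·b) − 1 = a/b − 1, so r cancels.

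**4. Illustration of size (all inputs assumed).** Take 18 complete pairs, no disease difference, and the non-lesional area in another region in half of them. The region shift is 0.5 or 1 SD of the pair difference, and the signed-rank test is two-sided at 5%.

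- Bias = fraction shifted × shift: 0.5 × 0.5 = 0.25 SD, and 0.5 × 1 = 0.5 SD.
- Simulated rejection with no shift: about 5%.
- Shifts in one direction: about 15% at 0.5 SD and about 40% at 1 SD.
- Shifts of the same size in random directions: about 5%.

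**5. Range with all 20 pairs shifted in one direction (4,000 simulated trials each).**

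| Shift (SD of pair difference) | 0 | 0.25 | 0.5 | 0.75 | 1.0 |
|---|---|---|---|---|---|
| Rejection, no disease difference | 5% | 18% | 55% | 87% | 99% |

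Expressed as a TEWL ratio between regions, with an assumed between-subject log-SD of 0.3 to 0.5, raw Week 16 values give:

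- ratio 1.10: 8% to 14%
- ratio 1.25: 25% to 58%
- ratio 1.5: 65% to 97%

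Percent change from own baseline stays at 4% to 5% throughout, as step 3 predicts.

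**6. Cost of restricting.** Under the step 4 assumptions 18 × 0.5 = 9 pairs remain. The standard error of the mean pair difference rises from SD/√18 = 0.24 SD to SD/√9 = 0.33 SD, a factor of √2 = 1.41.

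**The case against.** **The protocol may settle it.** Both patient areas are predefined, and how the non-lesional area is chosen is a measurement rule that a SAP may leave to the protocol. If that rule keeps it in the lesion's body region, there is no bias. This stands, and it makes the point conditional. It does not remove it: the SAP itself limits the matching to the lesion and then fixes comparisons that go beyond the matching.

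**The location-change rule is a different matter.** It concerns a spot that moves during follow-up, and it applies only when the study team judges the impact significant. It shows that the SAP accepts that location can affect the barrier. It does not show that the non-lesional and healthy areas differ materially. This also stands.

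**The analyses are exploratory.** The tests are additional ITT analyses, time to improvement is labelled exploratory, and section 5.6 predefines no hypothesis testing. That limits the weight of the point, but a mixed contrast misleads as an estimate too.

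**Two stronger readings are not supported.**

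- A reader might infer that the type-of-skin effect in the 4.3.3.1 model is distorted in the same way and needs a body-region covariate. That model analyses percent change from each area's own baseline, where a stable multiplicative site effect cancels, and the SAP states that no comparison will be made from it.
- A reader might infer that lesional versus non-lesional TEWL is confounded as well. No such TEWL test is planned. The lesional versus non-lesional contrast in section 2.5.1 of the biomarker SAP concerns biomarkers.

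**Conclusion.** The point holds in a limited form. The SAP matches healthy skin to the lesional location only, and uses it without adjustment as the reference for non-lesional skin in two sets of exploratory analyses: the raw Week 16 TEWL and TEWL AUC signed-rank tests, and the non-lesional time to improvement. Where the non-lesional area lies in another body region, these cannot separate disease from body site.

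The size is not known. It depends on the share of pairs with different regions, the shift between regions, and whether the shifts run in one direction. None of these is in the SAP. Under the assumptions tried it runs from no bias (same region throughout, or shifts that balance out) to 0.25 to 0.5 SD (half of the pairs shifted one way), and to more if all pairs are shifted.

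The primary endpoint is lesional and within patient, so it is not affected. The percent-change model is not materially affected. This is a cheap safeguard for interpretation and not a flaw in the main analysis.

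**What to change.** In sections 4.3.4 and 4.3.3.2 of the clinical SAP:

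1. Derive the body region of the lesional, non-lesional and healthy areas for each participant.
2. Report the number of pairs in which the non-lesional and healthy areas share a region.
3. Beside the planned results, give the non-lesional versus healthy Week 16 results (TEWL and TEWL AUC) and the non-lesional time to improvement restricted to those pairs.
4. Label the unrestricted contrast as not location-matched where regions differ. If the protocol fixes both areas in one region, a sentence saying so is enough.

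The cost is SAP wording and one derived variable. The areas are already predefined and photographed, so no new measurement is needed. The drawback is precision: few pairs may remain, so the restricted result is best read as an estimate with its interval. A non-significant test in that subset would not show that a difference is absent.
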